5.3 Dose Administration

All doses of investigational product will be administered via a 30-minute (± 10 minutes) peripheral or central IV infusion. During each 21-day treatment cycle, pembrolizumab will be administered first on Day 1 as a 30-minute (± 10 minutes) infusion. Sites should make every effort to target infusion timing to be as close to 30 minutes as possible. However, given the variability of infusion pumps from site to site, a window between -5 minutes and +10 minutes is permitted (i.e., infusion time is 30 minutes -5 min/+10 min). Birinapant will be administered 30 minutes (+10 minutes) following the completion of the pembrolizumab infusion. Birinapant will be administered alone on Day 8. A week without treatment (i.e., Days 15-21) will conclude each 21-day cycle, immediately after which the treatment cycle will be repeated (i.e., with pembrolizumab on Day 1 and birinapant on Days 1 and 8). Study drugs will be administered in the arm opposite to the site of blood-sample collection.

The birinapant dose will be administered according to the dose-escalation schedule and in the dose-expansion phase of the study, according to the RP2D that will be determined in the dose escalation phase of the study.

Dose Level	Pembrolizumab + Birinapant (per 21-day cycle)
Expansion	200 mg pembrolizumab on Day 1+ birinapant at the RP2D mg/m²/week on Days 1 and 8

The dose will be prepared by the site's Pharmacy and administered using materials known to be compatible with birinapant formulation. A filter should not be used during the birinapant infusion.

The birinapant dose calculation will be based on the patient's body surface area (BSA) using the Mosteller or institutional standard formula (to be calculated to the first decimal place) determined by height and weight at Screening (see the Pharmacy Manual). If a patient's BSA is > 2.5, then 2.5 will be used to calculate the patient's study-drug dose. If the patient's body weight has changed > 10% from that used to calculate the prior BSA, the BSA will be recalculated and the dose adjusted.

Pembrolizumab will be administered as a dose of 200 mg using a 30-minute IV infusion.

The pharmacy manual contains specific instructions for the preparation of the pembrolizumab infusion and administration of infusion solution. The dosing arm will be noted and all study blood samples for collection of safety and pharmacodynamic samples must be drawn from the contralateral arm.

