5.4 Dose-Limiting Toxicity and Recommended Phase 2 Dose

The inter-patient dose escalation of birinapant will be based on the number of patients that experience a DLT. A DLT is a clinically significant event attributed to birinapant, pembrolizumab, or the combination of the 2 study drugs, during the first cycle of drug therapy and is defined as follows:

Non-hematological toxicity:

- Common Toxicity Criteria for Adverse Event (CTCAE; 4.03) Grade 3 nausea, vomiting, or diarrhea despite maximal (according to treating investigator) anti-emetic or anti-diarrheal treatment and lasting > 48 hours; or Grade 4 vomiting or diarrhea;
- \geq Grade 3 other non-hematological toxicity, excluding isolated laboratory abnormalities without clinical sequelae, except for the following:
 - Prolonged (> 7 days) serum amylase or lipase elevation;
 - Prolonged (> 7 days) aspartate aminotransferase (AST) elevation;
 - Prolonged (> 7 days) alanine aminotransferase (ALT) elevation;All of which will be considered dose limiting.

Hematological toxicity:

- Grade 4 neutropenia;
- Grade \geq 3 neutropenia with fever > 38.3°C or > 38°C (> 100.9°F or > 100.4°F) for more than one hour;
- Grade \geq 3 thrombocytopenia with bleeding

Specific toxicity:

- Cytokine release syndrome (CRS); Grade 3 or 4. Furthermore, if a Grade >2 CRS occurs during the DLT period (Cycle 1), this also triggers the permanent discontinuation of all study dosing (birinapant AND pembrolizumab) with subsequent adequate care to treat the condition (see also sections 5.5.1 and 5.5.3).

If Day 8 of treatment is held due to toxicity then the event will be considered a DLT. A prolonged delay (> 2 weeks) in initiating Cycle 2 secondary to drug-related toxicity may be considered a DLT as judged by the SRC. Events related to disease progression, intercurrent illness, or concomitant medication will not constitute a DLT. Since patients are assessed for DLTs during the first cycle, dose modifications may not be performed. If a patient experiences a DLT that is deemed related to birinapant, the dose of birinapant may be restarted at a reduced level for Cycle 2 according to dose levels indicated in Table 2/[section 3](#) and the rules stated in [section 5.5](#), and the patient may remain on study.

The decisions to dose-escalate birinapant for each Dose Level are indicated in [Table 5](#) below.

Table 5 Escalation Decision Rules

Number of Patients with DLT at a Given Dose Level	Escalation-decision Rule

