The Investigational products will be administered as IV infusions by study staff and administration information will be recorded in the appropriate CRF.

The following variables will be derived for birinapant and Pembrolizumab separately:

- Cumulative dose = Sum of all administered doses.
- Treatment duration (weeks) = (Date of last dose – date of first dose + planned treatment duration(days))/7.
- Dose intensity = Cumulative dose/Treatment duration
- Relative dose intensity (%) = 100*Dose intensity/Planned dose intensity

Planned treatment duration(days) is 21 days for Pembrolizab and 13 days (21-8) for birinapant (this is the number of days between the last dose of a treatment cycle and the first dose in the subsequent cycle).

The unit of the dose will be in milligram (mg) for Pembrolizumab and in mg/m² for birinapant. For birinapant, the total dose in ‘mg’ is divided by the patient body surface area (m²) to get dose expressed as mg/ m².

Cumulative dose, treatment duration, dose intensity, relative dose intensity, number of infusions administered, number of cycles started, and infusion time per administration will be summarized using descriptive statistics by cohort, treatment (Pembrolizumab) and cycle (cycle 1 and the minimum and maximum observed value during the subsequent cycles) and in total over cycles as appropriate.

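### SAP 5.5.6 ends each drug's time base at its own last dose plus a fixed interval, so relative dose intensity only partly counts a missed final Day 8 birinapant dose and, if taken by cycle, cannot show a pembrolizumab delay

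*SAP*

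**What the plan says.** SAP 5.5.6 (Exposure to Study Treatment) opens with "The following variables will be derived for birinapant and Pembrolizumab separately" and gives the duration as "Treatment duration (weeks) = (Date of last dose – date of first dose + planned treatment duration(days))/7". Dose intensity is cumulative dose over that duration. Relative dose intensity is the ratio to planned dose intensity, which the SAP does not define.

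The added interval is fixed: "Planned treatment duration(days) is 21 days for Pembrolizab and 13 days (21-8) for birinapant". The SAP explains that "this is the number of days between the last dose of a treatment cycle and the first dose in the subsequent cycle". The results are to be summarised "by cohort, treatment (Pembrolizumab) and cycle (cycle 1 and the minimum and maximum observed value during the subsequent cycles", and also in total over cycles where appropriate. Number of infusions and number of cycles started are in the same list.

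The protocol sets the schedule (section 5.3): 21-day cycles with pembrolizumab on Day 1 and birinapant on Days 1 and 8. Section 5.4 foresees a lost Day 8 dose: "If Day 8 of treatment is held due to toxicity then the event will be considered a DLT". Section 5.5 permits no reduction of the pembrolizumab dose.

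**The concern.** Relative dose intensity is the summary a reader uses to judge whether the assigned regimen was delivered. Exposure is tabulated as part of the safety and tolerability analysis (Protocol 12.6). Two features of the formula work against that use.

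First, the birinapant interval is the gap from Day 8 to the next cycle. If the last dose given was a Day 1 dose, the clock stops about a week before the cycle ends. The lost dose leaves the numerator, but part of the time in which it was due leaves the denominator as well.

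Second, pembrolizumab is given once per cycle. Within one cycle the first and last dose are the same dose, so the duration is a constant. Because the dose cannot be reduced, delay is the main way its intensity can fall, and a by-cycle figure built on this formula cannot register delay.

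**Working it through.** **Inputs.** Schedule from Protocol 5.3; formula and intervals from SAP 5.5.6. Assumption: planned intensity is 2 assigned doses per 21 days for birinapant and 200 mg per 3 weeks for pembrolizumab. The first dose is day 0, and doses fall on schedule unless stated.

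**1. The plan's own intervals.** Pembrolizumab: Day 22 − Day 1 = 21, which reproduces. Birinapant: Day 22 − Day 8 = 14, so 13 does not reproduce. Counting only the days strictly between gives 13 for birinapant, but then 20 for pembrolizumab. No single convention gives both 21 and 13.

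**2. Birinapant, final Day 8 dose missed.** With d doses over D days, relative intensity = 100 × (d/D)/(2/21). After k cycles, d = 2k − 1 and D = 21(k − 1) + 13. A fully dosed patient has d = 2k and D = 21(k − 1) + 7 + 13.

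| Cycles | Final Day 8 missed, SAP (13 days) | Fully dosed, SAP (13 days) | Final Day 8 missed, 14 days | Share of planned doses given |
|---|---|---|---|---|
| 1 | 1/13 → 80.8% | 2/20 → 105.0% | 1/14 → 75.0% | 1/2 = 50% |
| 2 | 3/34 → 92.6% | 4/41 → 102.4% | 3/35 → 90.0% | 3/4 = 75% |
| 3 | 5/55 → 95.5% | 6/62 → 101.6% | 5/56 → 93.8% | 5/6 = 83.3% |

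With 14 days a fully dosed patient reads 100% throughout.

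**3. How much of the shortfall is hidden.** Against 100%: (80.8 − 50)/50 = 62%, (92.6 − 75)/25 = 71%, (95.5 − 83.3)/16.7 = 73%. Against the formula's own fully dosed value, the drop is 24.2 of 50, 9.8 of 25 and 6.2 of 16.7 points, so 52%, 61% and 63% is hidden. Roughly half to three quarters is lost, least after one cycle.

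**4. Dependence on which dose is missed.** Three cycles, 5 of 6 doses:
- Cycle 2 Day 8 missed: the last dose is on day 49, D = 49 + 13 = 62, and 100 × (5/62)/(2/21) = 84.7%.
- Cycle 3 Day 8 missed: the last dose is on day 42, D = 42 + 13 = 55, giving 95.5%.

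The number of doses delivered is the same.

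**5. Pembrolizumab.** By cycle: duration = (0 + 21)/7 = 3 weeks, and (200/3)/(200/3) = 100% for any complete infusion, however late the next cycle starts. In total, for two doses 6 weeks apart: duration = (42 + 21)/7 = 9 weeks, and (400/9)/(200/3) = 66.7%. The total therefore does show the delay.

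**6. Sensitivity to the assumption.** If planned birinapant intensity were 2 doses per 20 days, matching the 13-day constant, the missed-final-dose figures would be 76.9%, 88.2% and 90.9%. They still lie above 50%, 75% and 83.3%.

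**The case against.** The strongest case against is that little depends on this. Exposure is descriptive, the only formal analysis is of ORR (SAP 5.6), and no stated decision rule uses relative dose intensity. The lost dose also shows elsewhere: one birinapant infusion alongside one cycle started reveals it. A Day 8 dose held for toxicity is itself a DLT, and DLT incidence is reported (Protocol 12.6). All of this stands, and it limits the severity.

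It can also be said that the by-cycle result depends on how the SAP is read. The variables are defined over the whole course, no per-cycle duration formula is given, and some listed items make little sense by cycle. That is fair, so the pembrolizumab point is conditional on applying the formula by cycle. The SAP does, however, list by-cycle summaries of these variables and offers no other formula.

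Three stronger readings are tempting and not supported:
- That the measure looks best for patients who lost a dose and stopped. It is inflated for them, but they still read below fully dosed patients on the same scale (80.8% against 105.0% after one cycle).
- That pembrolizumab delays are invisible. The total over cycles registers delays between doses.
- That a patient correctly dosed at the cap on body surface area must appear under-dosed. The SAP says the dose in mg "is divided by the patient body surface area" without saying which value. Protocol 5.3 caps it (above 2.5, "then 2.5 will be used to calculate" the dose), and SAP Table 5, footnote 5, repeats the cap, so a programmer could well use the dosing value. This calls for a clarification only.

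**Conclusion.** The concern holds as a minor point about a descriptive derivation. Under the stated assumption on planned intensity, a missed final Day 8 birinapant dose is reported at 80.8%, 92.6% and 95.5% after one to three cycles, where 50%, 75% and 83.3% of planned doses were given. Identical delivery can read 84.7% or 95.5% depending only on which Day 8 dose was lost.

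The 13-day constant is a separate inconsistency that lifts fully dosed patients above 100%. Changing it to 14 cures that but not the under-counting, which comes from tying the end of the clock to the last dose given. By cycle, the pembrolizumab figure is uninformative about delay, provided the infusion was complete and the formula is applied as listed.

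The ORR test is unaffected, and infusion and cycle counts remain available to a careful reader.

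**What to change.** In SAP 5.5.6:
- Define total duration for both drugs as (Day 1 of the last cycle started − Day 1 of Cycle 1 + 21)/7.
- For by-cycle figures, use the actual days to the next cycle's Day 1, and 21 for the last cycle.
- Define planned intensity as 200 mg per 3 weeks for pembrolizumab and 2 × the assigned mg/m² per 3 weeks for birinapant.
- As a clarification, state that birinapant mg/m² is obtained with the body surface area, cap included, from which that dose was calculated.

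With this definition the three birinapant cases read 50%, 75% and 83.3%, and 5 of 6 doses over three on-schedule cycles give 83.3% whichever Day 8 is missed (5 doses over 63 days). The cost is a change of SAP wording and of the derived duration, using dosing dates already collected. The downside is that a patient who stops mid-cycle for any reason, including progression or death before Day 8, is counted as having been due the full 21-day cycle. A footnote to the table can say so.

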5.5.7 Premature Termination

Patients who terminated prematurely will be summarized by reason for early termination and cancer cohort.

5.6 Efficacy Analyses

The only formal statistical analysis in the study concerns the ORR, assessed through RECIST 1.1, in each of the three main cancer cohort in the dose expansion phase of the study. That analysis is detailed in Section 5.6.1. The remaining efficacy endpoints will be summarized using descriptive statistics in accordance with Section 5.3 if other not stated.

5.6.1 Primary Efficacy Analysis

The primary endpoint will be summarized for the Efficacy Evaluable Population in accordance with Section 5.3.

The primary efficacy analysis for each of the three main cohorts in the dose expansion phase of the protocol will be evaluated using Simon’s two-stage design (Simon 1989). The null hypothesis that the true response rate (π) is π_0 will be tested against the one-sided alternative $H_A: \pi > \pi_0$ in each of the three cohorts with π_0 , π_1 , n_1 , n , r_1 and r_2 as in Table 4 as follows. In the first stage, n_1 patients will be accrued. If there are r_1 or fewer responses in these n_1 patients, the cohort will be stopped and the p-value for the test will be reported as not significant (no p-value will be calculated). Otherwise, $n - n_1$ additional patients will be accrued for a total of n patients. The null hypothesis will be rejected if r_2+1 or more responses are observed in n patients.

Table 4 Simon’s two-stage design settings in each of the three main cohorts

Indication	Response rate (ORR)		n_1 (# patient in the 1 st stage)	n (Total #patients)	r_1 (Continue with stage 2 if $>r_1$ responses in stage 1)	r_2 (p-value ≤ 0.05 if $>r_2$ responses after stage 2)
	Poor drug (π_0)	Good drug (π_1)				
Colorectal cancer	$\leq 5\%$	$\geq 20\%$	13	27	0	3

Ovarian cancer	$\leq 7\%$	$\geq 25\%$	16	26	1	4
Cervical cancer	$\leq 10\%$	$\geq 30\%$	15	25	1	5

In case the total number of evaluable patients do not equal the planned number of patients (n in Table 4), the statistical inference of the ORR will take account of the actual total number of evaluable patients, n^* , as suggested in Koyama and Chen (2007). With a modified stage 2 sample size, the p-value will be calculated as follows.

- i. Find π^* such that $P_{\pi}(X_2 > r_2 - x_1 | n_2) = P_{\pi_0}(X_2 \geq x_2 | n_2^*)$
- ii. Compute the p-value by

$$\sum_{x=r_1+1}^{n_1} P_{\pi_0}(X_1 = x | n_1) A(x, n_2, \pi^*)$$

Here $n_2 (= n - n_1)$ denotes the planned number of patients in the second stage, n_2^* the actual number of patients in the second stage and X_2 denotes the number of responses among those n_2 patients. The p-value will be calculated as above even if $n_2^* = n_2$. In that case it simplifies to the original Simon's 2-stage design with rejection regions as in Table 4.

The point estimate of response rate and the corresponding 90% confidence interval will be obtained by inverting the hypothesis testing. Compute the p-value for testing $H_0: \pi \leq \pi'_0$ versus $H_A: \pi > \pi'_0$ as above. The 90% confidence interval for π is the collection of π'_0 such that the corresponding p-value is within [0.05, 0.95]. The value of π'_0 which gives a p-value of 0.5 will be the point estimate of the response rate (π).

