The primary objective will be evaluated using Simon's two-stage design. The null hypothesis that the true ORR is (5%, 7% and 10% for colorectal cancer, ovarian cancer and cervical cancer, respectively) will be tested against a one-sided alternative. The design yields a type I error rate of 5% and power of 80% for each of the three indications individually. No correction for multiplicity will be done. In addition to tabulate the result of the statistical tests, results will be summarized descriptively.

Various solid tumors cohort: Safety

The safety and tolerability of pembrolizumab and birinapant will be based on results of reported SAEs, AEs, vital sign measurements, physical examinations, clinical laboratory information, ECOG performance status, and concomitant medications. Safety data will be summarized descriptively. Exposure to study drug and reasons for discontinuation will be tabulated.

Adverse events will be coded using the current *Medical Dictionary for Regulated Activities* (MedDRA) classification system, and will be summarized by system organ class and preferred term.

Additional safety analyses may be determined in order to most clearly describe toxicity rates and to further define the

safety profile of pembrolizumab and birinapant.

Secondary Endpoints:

Cohorts in colorectal cancer, ovarian cancer and cervical cancer: Safety

The safety and tolerability of pembrolizumab and birinapant will be based on results of reported SAEs, AEs, vital sign measurements, physical examinations, clinical laboratory information, ECOG performance status, and concomitant medications. Safety data will be summarized descriptively by cohort and also summarized descriptively over cohorts within each of the two phases of the protocol. Exposure to study drug and reasons for discontinuation will be tabulated.

Adverse events will be coded using the current *Medical Dictionary for Regulated Activities* (MedDRA) classification system, and will be summarized by system organ class and preferred term.

Additional safety analyses may be determined in order to most clearly describe toxicity rates and to further define the safety profile of pembrolizumab and birinapant.

All Cohorts: Clinical Activity

Efficacy, as defined by PFS, CBR, Time to response and Duration of response, will be assessed through RECIST v 1.1 and until response or progression. Overall survival will also be assessed.

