3.3.1.2 Dose expansion phase

The dose expansion phase will comprise 4 cohorts of 26-30 patients, as follows:

1. Colorectal cancer (28 patients will be recruited)
2. Ovarian cancer (27 patients will be recruited)
3. Cervical cancer (26 patients will be recruited)
4. Various solid tumors (30 patients will be recruited, including 5 patients with each of the 6 following tumor types: (Small cell lung cancer; Cholangiocarcinoma; Gastroesophageal carcinoma; Mesothelioma; Head and Neck Squamous Cell Carcinoma (HNSCC)-checkpoint inhibitor-naïve; and HNSCC checkpoint inhibitor-experienced)

A Simon's 2-stage design (Simon 1989) will be used for each of the cohorts in colorectal cancer, ovarian cancer and cervical cancer, as outlined in Table 4. A predefined interim analysis allowing stopping each of these cohorts for futility and safety will be conducted in the first stage to limit undue exposure before further inclusion into a given cohort.

The interim analyses will be based on at least 6 and most 13 patients having completed from 9 up to 27 weeks of treatment (3 to 9 cycles) in the colorectal cancer cohort and based on at least 6 and at most 16 and 15 patients in the ovarian cancer cohort and cervical cancer cohort, respectively.

The Simon's two-stage design as outlined in Table 4 yields a type I error rate of 0.05 and statistical power of 0.80 for each of the three main cohorts described above using a one-sided test when the true response rate is 20% for colorectal cancer, 25% for ovarian cancer and 30% for cervical cancer. No formal sample size or power calculation will be performed for the fourth cohort.

Note that one additional patient will be included in each cohort compared to what is stated in Table 4. This patient will only be included in the interim analysis in case a patient drops out in that cohort. Thus, the number of included patients in each cohort will be 27+ 1 (CRC), 26+1 (ovarian) and 25+1 (cervical). In all cases this extra patient will be included in the main/end analysis. If the predefined level for success in a given cohort is reached prior to the stipulated number of patients being enrolled/completed, enrollment in that cohort may be discontinued.

4. Assessments

An overview of the time points of measurements for each assessment is given in Table 5 (Schedule of Study Procedures and Assessments) in Appendix 1.

4.1 *Disposition and Other Supporting Assessments*

4.1.1 *Patient Compliance*

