5.3 General Principles for Presenting Study Data

All statistical analyses will be performed at SDS using SAS® (Version 9.3 or higher, SAS Institute Inc., Cary, NC, USA). All statistical analyses will be performed after this SAP is finalised and approved and the study database is locked.

Continuous data will be summarized using descriptive statistics where the following parameters will be reported:

- Number of observations (n),
- Mean,
- Median,
- Standard deviation (SD),

- Range (Min, Max)

Categorical data will be presented as the number and percentage of patients.

Time to event endpoints defined in Section 4.2.3 (e.g. duration of response, OS and time to iCPD) will be analysed using Kaplan-Meier methods taking censoring into account. The Kaplan-Meier plot and corresponding estimate of the median value with 95% confidence interval will be reported.

All tests will be one-sided and performed at the 5% significance level. When reporting the results of significance tests, p-values will be reported together with 2-sided 90% confidence intervals.

Throughout the report, the number of decimal places given for the summary statistics; mean, STD, confidence interval and median values will exceed that of the source data by one. Minimum and maximum will have the same number of decimal places as the source data. For relative frequencies, integer with one decimal and %-sign will be presented and for p-values four (three) decimals will be reported.

Percentages will be based on number of patients with data at a certain time point with the exception of presentations of medical history, medications and AEs where the percentages will be based on the number of patients in the study population.

In general, all data will be listed, sorted by phase of study, cohort and patient, and when appropriate by cycle within patient. All summary tables will be structured with a column for cohort and will be annotated with the total population size relevant to that table/cohort, including any missing observations. Summary tables will include summaries for visits for Cycle 1 (Screening, Day 1 pre dose, Day 1 post dose, Day 8 pre dose, Day 8 post dose and Day 22 End of Cycle 1 as appropriate) whereas subsequent cycles will be summarized with summary statistics for the minimum and maximum observed value during the subsequent cycles.

The two phases of the study will be summarized separately. In addition, cohorts from phase 1 and phase 2 may be combined and summarized if appropriate.

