5.4.3.1 Colorectal Cancer Cohort

The interim analysis will be based on at least 6 and most 13 patients having completed from 9 up to 27 weeks of treatment (3 to 9 cycles) in the colorectal cancer cohort.

The second stage will continue, i.e. the remaining patients in the cohort will be recruited according to the plan, if at least 1 patient (out of 6-13 patients) responds in the overall tumor response assessed through RECIST v1.1. (provided the DMC decides not to stop the second stage because of safety issues).

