5.6.5 Sensitivity Analyses

A sensitivity analysis of the primary endpoint will be conducted if there are patients that are wrongly included into the study and receives a dose of pembrolizumab and birinapant. In that case, the primary efficacy analysis will be repeated when those patients are excluded from the efficacy evaluable population, for the cohorts it concerns, as a sensitivity analysis. Also other major protocol deviations may be considered in this sensitivity analysis.

5.7 *Safety Analyses*

No formal statistical analyses will be performed, although descriptive summaries for continuous data and for categorical data will be provided in accordance with Section 5.3 if other not stated. Complete listings of all patient safety evaluations will be provided to support each summary table.

All presentations will be based on the safety analysis set.

5.7.1 *Adverse Events*

Adverse Events (AEs) will be coded by system organ class (SOC), preferred term (PT) and Verbatim name using MedDRA Version 20.0

All AEs will be listed whereas the treatment emergent AEs (TEAEs), i.e. any AE with onset or worsening on or after the first dose of any IMP and within 30 days after the last dose of IMP, will be summarized as follows. The number of TEAEs, as well as the number and percentage of patients reporting any TEAE will be summarised for Cycle 1, subsequent cycles and Safety follow-up by cohort. Separate summary tables will be produced for the following:

1. TEAEs related to IMP by Verbatim names
2. TEAEs related to IMP by SOC and PT
3. TEAEs not related to IMP by Verbatim name
4. TEAEs not related to IMP by SOC and PT
5. Serious Adverse Events (SAEs) by Verbatim name
6. SAEs by SOC and PT.
7. TEAEs related to IMP by AE grade
8. TEAEs not related to IMP by AE grade

AEs leading to withdrawals or death will be presented by cohort.

All percentages will be based on the number of patients in the safety set.

5.7.2 *Clinical Laboratory Tests*

All laboratory parameters for individual patients will be listed and patients with abnormal values (out of normal range reported by the laboratory) and with clinically significant abnormalities (according to the Investigator's criteria) will be flagged.

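### The SAP p-value adapts stage 2 but keeps the planned stage 1, so after a smaller interim that the SAP allows, a response count at the Table 4 boundary can give p above 0.05

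*SAP*

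**What the plan says.** SAP 5.6.1, Table 4, sets n1, n, r1 and r2 at 13, 27, 0, 3 (colorectal), 16, 26, 1, 4 (ovarian) and 15, 25, 1, 5 (cervical). The null hypothesis is rejected at r2+1 or more responses in n patients, and the last column header equates this with p at or below 0.05.

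For a total that differs from n, the section continues: "With a modified stage 2 sample size, the p-value will be calculated as follows". Step i finds a rate π* from the observed second stage, using its actual size n2*. Step ii sums over stage 1 outcomes from r1+1 to n1. In both steps n1 and n2 = n − n1 are the planned sizes. The formula is also to be used when n2* equals n2. The next paragraph obtains the point estimate and 90% interval by inverting this p-value.

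SAP 5.4.3 says that the interim is the first stage of the design. For colorectal cancer, "The interim analysis will be based on at least 6 and most 13 patients having completed" 9 to 27 weeks of treatment. The ranges are 6-16 for ovarian and 6-15 for cervical cancer, and the continuation thresholds stay at r1+1. SAP 3.3.1.2 adds one patient per cohort, who always enters the final analysis, so the final totals are 28, 27 and 26. No section says what replaces n1 when fewer than n1 patients are analysed at the interim.

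**The concern.** When the interim uses m < n1 patients and recruitment then runs to plan, the n1 − m patients missing from stage 1 are counted in n2*. In step i the larger n2* makes the same number of stage 2 responses less surprising. Step ii still gives the trial a full-size stage 1. The result describes a design that was not run, and it errs towards larger p-values.

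This is the only formal test in the study (SAP 5.6). A cohort that reaches the planned success count could be reported as non-significant, with an interval and estimate shifted downwards.

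**Working it through.** **Inputs.** "All tests will be one-sided and performed at the 5% significance level" (SAP 5.3). The null rates are "5%, 7% and 10% for colorectal cancer, ovarian cancer and cervical cancer, respectively" (protocol synopsis). The design "yields a type I error rate of 0.05 and statistical power of 0.80 for each of the three main cohorts" (SAP 3.3.1.2), "when the true response rate is 20% for colorectal cancer, 25% for ovarian cancer and 30% for cervical cancer". The SAP does not define A(x, n2, π*). I read it as P(X2 > r2 − x | n2, π*), which matches the left side of step i.

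**The plan's own figures.** P(reject) = Σ over x = r1+1..n1 of P(X1 = x | n1) · P(X2 > r2 − x | n2):

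| Cohort | Type I error | Power |
|---|---|---|
| Colorectal | 0.0416 | 0.801 |
| Ovarian | 0.0306 | 0.803 |
| Cervical | 0.0328 | 0.802 |

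These agree with the stated 0.05 cap and 0.80. With planned sizes the SAP p-value at r2+1 responses returns exactly these type I errors, which supports the reading of A.

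**One case in full.** Colorectal, 12 at the interim with 1 response, then 3 responses in 28 − 12 = 16, so 4/28.

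- Step i: P(X2 ≥ 3 | 16, 0.05) = 0.0429. Solving P(X2 > 2 | 14, π*) = 0.0429 gives π* = 0.0575.
- Step ii as written (n1 = 13): 0.3512 × 0.0429 + 0.1109 × 0.1908 + 0.0214 × 0.5635 + 0.0031 × 1 = 0.0514.
- With actual sizes (stage 1 = 12, stage 2 = 27 − 12 = 15): π* = 0.0535, and 0.3413 × 0.0429 + 0.0988 × 0.1899 + 0.0173 × 0.5616 + 0.0022 × 1 = 0.0454.

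**Boundary count r2+1 with the extra patient** (ranges are over x1, the number of interim responses):

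| Result | At interim | SAP p | p with actual sizes |
|---|---|---|---|
| Colorectal 4/28 | 12 | 0.051 | 0.045 |
| Colorectal 4/28 | 10 | 0.060-0.062 | 0.042-0.043 |
| Colorectal 4/28 | 6 | 0.082-0.085 | 0.033 |
| Ovarian 5/27 | 12 | 0.053-0.056 | 0.029 |
| Cervical 6/26 | 13 | 0.050-0.054 (lowest 0.0502) | 0.037 |
| Cervical 6/26 | 10 | 0.071-0.080 | 0.032 |

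**Interim sizes at which p exceeds 0.05 at r2+1:**

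| Cohort | Total n+1 | Total n |
|---|---|---|
| Colorectal | 6-12 | 6-11 |
| Ovarian | 6-12 (13 if x1 = 2) | 6-11 (12 if x1 = 2) |
| Cervical | 6-13 | 6-12 |

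**Power at the target rate**, rejecting at r2+1 against rejecting at SAP p ≤ 0.05 (x1 > r2, where step i has no solution, is counted as rejection):

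| Case | r2+1 rule | SAP p rule |
|---|---|---|
| Colorectal, 28 total, 12 at interim | 81.2% | 67.5% |
| Colorectal, 28 total, 10 at interim | 78.6% | 65.6% |
| Cervical, 26 total, 13 at interim | 81.7% | 69.5% |
| Colorectal, 27 total, 12 at interim | 79.35% | 79.35% |
| Cervical, 25 total, 13 at interim | 79.05% | 79.05% |

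In the first row the type I error is 0.045 under the r2+1 rule and 0.012 under the SAP p-value.

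**Interval.** For colorectal 4/28 with 10 at the interim, the 90% interval is 4.7-24.7% as written and 5.3-28.6% with the actual sizes. Only the second excludes the 5% null.

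**The case against.** **Stage 1 could mean the first n1 patients accrued.** SAP 5.6.1 says n1 patients are accrued in the first stage. If the interim merely looks at those assessable so far, n2* equals n2 at total n and nothing goes wrong. But SAP 5.4.3 equates the interim with the first stage and decides continuation on the interim patients, so this reading is possible but not the one the SAP states.

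**Any interim below n1 produces the conflict.** A reader might infer this, but it is too broad. With exactly n patients, colorectal 12, ovarian 13-15 and cervical 13-14 are clear. The near-plan power losses exist only with the extra patient, who is however planned.

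**Two rules compete.** With 28, 27 or 26 patients, 5.6.1 sends the analysis to the p-value, so the harm there is lost power, not two verdicts. With exactly n patients and a short interim, the r2+1 rule and the p-value do contradict each other.

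**Exclusions under SAP 5.6.5.** There "the primary efficacy analysis will be repeated when those patients are excluded from the efficacy evaluable population". A reader might infer that removing stage 1 patients has the same effect. It does not: excluded patients leave the analysis and do not move to stage 2, so n2* is unchanged. The p-value at r2+1 stays at 0.0416, 0.0306 and 0.0328, or at most 0.0464, 0.0352 and 0.0393 with the extra patient.

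**Correcting the sizes does not by itself align the two rules.** This stands. At very small interims the corrected p-value can be at or below 0.05 at r2 or fewer responses. With total n this happens for ovarian 6-9 and cervical 6-7; for example, ovarian 4/26 with 6 at the interim and x1 = 2 gives 0.0268, where Table 4 needs 5.

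**Conclusion.** The p-value in SAP 5.6.1 is wrong as written for interims smaller than n1 and should be corrected. The evidence does not support treating it as a threat to the trial's validity. Type I error is never inflated. The excess over 0.05 occurs almost only at r2+1 responses; at r2+2 it appears only for cervical interims of 6, and of 7 with the extra patient. Where it bites near plan, it costs about 12 to 14 percentage points of power (81.7 − 69.5 = 12.2; 81.2 − 67.5 = 13.7) with no gain that the 5% target needs.

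This rests on four assumptions: the interim patients are stage 1; all others are stage 2; A is read as above; and the interim size is unrelated to outcome. The last is not guaranteed, because protocol 3.1.4 lets the DMC delay the interim on investigators' judgement of patient benefit. The lower power of very small interims under the unchanged futility thresholds is a separate matter and is not counted here.

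**What to change.** In SAP 5.6.1:

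- Define stage 1 as the patients analysed at the interim, and call their number n1*.
- In steps i and ii, and in the inversion for the estimate and interval, replace n1 by n1* and n2 by n − n1*. Keep r1 and r2.
- Define A(x, n2, π*), and say how x1 > r2 is handled.
- State which single rule governs the conclusion whenever actual sizes differ from Table 4.

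With these sizes, p at r2+1 responses is at or below 0.05 at every allowed interim size, for total n or n+1. If the corrected p-value governs, its exact type I error is at most 0.048 over all allowed interim sizes.

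The cost is SAP wording and one code parameter, with no new data. The change should be made before database lock, so that the rule is not chosen after the response counts are known.
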